#### Phase II

With a one-stage Fleming design,  $\alpha = 5\%$ ,  $\beta = 20\%$ ,  $p_0$  (the probability of inefficiency maximum) = 35% and  $p_1$  (the probability of minimum efficiency) = 50%, it would be necessary to include 65 evaluable patients (69 patients/ 5% non-evaluable patients).

The association can be considered sufficiently effective (reject null hypothesis) if there are at least 29 success (48 weeks disease control rate) out of 65 evaluable patients, the success rate is significantly greater than 35%.

The association can be considered insufficiently effective (reject alternative hypothesis) if there are 28 or less success out of 65 evaluable patients, the success rate is significantly lower than 50%.

In total, a maximum of 87 (=18 patients for phase I + 69 patients for phase II including 6 patients treated at the RP2D during the phase I) patients will be included.

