### **Phase II :**

The 6 patients treated at the RP2D in the phase I part will be included in the phase II part. The multicenter, phase II trial is planned to enroll 69 patients. The patients who meet the study eligibility criteria will be included to receive the study drug.

- ❖ **First inclusion:** april 2019
- ❖ **Inclusion period:** 12 months Phase I + 12 months Phase II
- ❖ **End of the inclusion period:** march 2021
- ❖ **Expected end of study:** june 2022
- ❖ **Report:** september-december 2022
- ❖ **Poster/public:** phase I (2020), phase II (april 2023 and july 2023)

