### 10.2. STUDY POPULATIONS

Different population of patients may be defined for the analysis:

- Intent To Treat (ITT) population: all included patients.
- Per-Protocol (PP) population: all eligible patients (patients with no major violations of the inclusion/exclusion criteria) and evaluable patients (included treated patients with evaluation at 48 weeks or without evaluation at 48 weeks if progressive or dead patient).
- Safety population: all treated patients who received at least one dose of treatment.

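### The phase II go/no-go count is defined only for exactly 65 evaluable patients although 69 are enrolled, and it does not hold the stated 5% error at 65 or at any larger number

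*Combined protocol and SAP*

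**What the plan says.** Section 10.1 (Phase II), repeated in the synopsis, starts "With a one-stage Fleming design" with α = 5%, β = 20%, p0 = 35% and p1 = 50%. It concludes that "it would be necessary to include 65 evaluable patients (69 patients/ 5% non-evaluable patients" are needed. The go rule applies "if there are at least 29 success (48 weeks disease control rate) out of 65 evaluable patients"; the no-go rule applies "if there are 28 or less success out of 65 evaluable patients". Section 3.1 confirms that the "phase II trial is planned to enroll 69 patients", a figure that includes the six phase I patients treated at the recommended dose.

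Evaluability, within the per-protocol definition of Section 10.2, covers "included treated patients with evaluation at 48 weeks or without evaluation at 48 weeks if progressive or dead patient". Two other denominators are in play: Section 2.2.1 defines the 48-week disease-control rate over treated patients, and the ITT set in Section 10.2 is everyone included.

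No section gives a cut-off for a number other than 65, limits the decision to the first 65 evaluable patients, or says how to rescale. Section 10.3 describes the primary endpoint by a percentage with a 95% confidence interval. It leaves further detail to a statistical analysis plan to be written before the database closes.

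**The concern.** A single integer cut-off has its stated error rates at one sample size only. Evaluability depends on what has happened by week 48, so 65 cannot be hit by design. On the treated or included sets the number may be as high as 69. The analyst would then have to keep 29, scale the proportion 29/65, cut the set to 65, or redo the test. These options can give opposite verdicts on the same data, and the trial has no control arm to fall back on. At stake is the type I error of the only formal decision in phase II, and whether a result near the boundary can be reported as the outcome of a rule set in advance.

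**Working it through.** **Inputs.** p0 = 0.35, p1 = 0.50, α = 5%, β = 20%, 65 evaluable, 69 enrolled, 5% non-evaluable and the cut-off of 29, all from Section 10.1. The plan does not state sidedness. One-sided is assumed, because two-sided 5% would need 82 patients.

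**1. The plan's sample size.** Normal approximation: n = [(1.645·√(0.35·0.65) + 0.842·√(0.50·0.50)) / 0.15]² = 64.57, so 65. Then 65/0.95 = 68.4, so 69. Both figures reproduce.

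**2. The plan's cut-off.** The approximate bound at 65 is 65·0.35 + 1.645·√(65·0.35·0.65) = 29.08. The printed 29 lies just below it. Exact binomial: P(X ≥ 29 | 65, 0.35) = 6.9%, with power P(X ≥ 29 | 65, 0.50) = 83.9%. A cut-off of 30 gives 4.1% and 77.1%. So the printed rule does not have a 5% exact error even at 65.

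**3. How often the number is 65.** Taking the number evaluable as Binomial(69, 0.95): P(exactly 65) = 19.3%, P(more) = 54.5%, P(fewer) = 26.2%. The first figure depends on the rate, but never exceeds about 20% (its peak is near 4/69, or 5.8%).

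**4. Three ways to decide at other N.** The entries are the exact type I error P(X ≥ r | N, 0.35) for the cut-off r shown. Scaled means 29N/65 rounded up. Exact means the smallest r with error at most 5%; its power at 50% is in the last column.

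| N | P(N) | keep 29 | scaled | exact | power, exact |
|---|---|---|---|---|---|
| 61 | 1.4% | 2.9% | 28: 5.1% | 29: 2.9% | 69.6% |
| 62 | 3.5% | 3.7% | 28: 6.3% | 29: 3.7% | 73.7% |
| 63 | 7.4% | 4.6% | 29: 4.6% | 29: 4.6% | 77.5% |
| 64 | 13.2% | 5.7% | 29: 5.7% | 30: 3.3% | 73.4% |
| 65 | 19.3% | 6.9% | 29: 6.9% | 30: 4.1% | 77.1% |
| 66 | 22.2% | 8.3% | 30: 5.1% | 31: 3.0% | 73.1% |
| 67 | 18.9% | 9.9% | 30: 6.2% | 31: 3.7% | 76.8% |
| 68 | 10.5% | 11.7% | 31: 4.6% | 31: 4.6% | 80.2% |
| 69 | 2.9% | 13.7% | 31: 5.6% | 32: 3.4% | 76.5% |

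Averaged over Binomial(69, 0.95), type I error is 8.0% keeping 29, 5.7% scaled and 3.7% exact. Average power under the exact rule is about 76%.

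**5. Does the choice change a verdict?** At N = 69 the three rules need 29, 31 and 32. A count of 29 to 31 passes the first and fails the third. The probability of such a count is 10% if the true rate is 35%, about 28% at 42% or 45%, and 16% at 50%.

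**The case against.** Several points against the concern are sound.

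- A reader might infer that enrolling 69 lifts the error from 5% to 8–14%. The documents do not support that. The starting point at 65 is 6.9%, so of the average excess over 5%, 1.9 points (6.9 − 5.0) come from the cut-off itself and 1.1 points (8.0 − 6.9) from the varying number. The 13.7% needs all 69 to be evaluable, which has probability 2.9% at the plan's rate. Below 65, keeping 29 lowers the error.
- The plan never says that 29 is kept at 66 to 69. That is one reading, and the least favourable of those calculated. Scaling stays at or below 6.3% for N of 61 to 69, other than the 6.9% at 65 itself.
- The 19/54/26% split describes an evaluable set only. On the treated or included sets the number would be at or near 69 and would vary little. The mismatch with 65 remains there, but as a conflict of denominators.
- A reader might also infer that the rule would be chosen with the count already known. The trial is open-label, but success is counted after central review, and the analysis plan promised in Section 10.3 could set cut-offs in time. Late choice is a risk, not something the documents show.
- A pre-specified set of the first 65 evaluable patients would also give a single valid number.

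What stands is that the text supplied has no rule for any number but 65, and that the count it prints misses 5% at 65 and above.

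**Conclusion.** The concern holds in a limited form. The decision rule covers one sample size that an evaluable set reaches in roughly one trial in five, and the printed count has an exact type I error of 6.9% there. If 29 is carried to other numbers, the error runs from 2.9% at 61 to 13.7% at 69 and averages 8.0%; scaling averages about 5.7%. Near the boundary the conclusion therefore turns on an unstated choice. The averages assume a one-sided test and independent non-evaluability at 5%; the errors at each N need only the one-sided test and p0 = 35%. This should be corrected, but it does not invalidate the design, and the later analysis plan could still close the gap.

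**What to change.** In Section 10.1 and the synopsis, replace the single count by a rule for the number actually analysed in the declared primary set: reject 35% if the exact one-sided binomial p-value is at most 5%. Print the resulting minimum counts: 29 for 61–63 patients, 30 for 64–65, 31 for 66–68 and 32 for 69. Outside that range the p-value rule itself applies. Name the primary set in the same sentence, and settle both before outcome data are reviewed.

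The text change is one sentence and one small table, with no new patients or data. The statistical cost must be stated with it. Average type I error becomes about 3.7%. Power at 50% averages about 76%, lies between 73% and 80% for 64 to 69 patients, and reaches 80% only at 68. The stated 80% power should be restated accordingly. If the sponsor prefers a fixed set of the first 65 evaluable patients, the exact cut-off there is 30, with 4.1% error and 77.1% power.

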STATISTICAL CONSIDERATIONS	
Phase I
 
A minimum of 12 and a maximum of 24 patients will be included. The dose escalation corresponding to a minimum of 3 and a maximum of 6 patients per dose level.
 
A total of 6 patients will be included at the RP2D.
 
Phase II
 
With a one-stage Fleming design, <math>\alpha = 5\%</math>, <math>\beta = 20\%</math>, <math>p_0</math> (the probability of inefficiency maximum) = 35% and <math>p_1</math> (the probability of minimum efficiency) = 50%, it would be necessary to include 65 evaluable patients (69 patients/ 5% non-evaluable patients).
 
The association can be considered sufficiently effective (reject null hypothesis) if there are at least 29 success (48 weeks disease

STATISTICAL CONSIDERATIONS	
control rate = CR / PR / SD) out of 65 evaluable patients, the success rate is significantly greater than 35%. The association can be considered insufficiently effective (rejection of the alternative hypothesis) if there are 28 or less success out of 65 evaluable patients, the success rate is significantly lower than 50%.
 
In total, a maximum of 87 (=18 patients for phase I + 69 patients for phase II including 6 patients treated at the RP2D during the phase I) patients will be included.
 
Analysis population
 
Intent To Treat (ITT) population = all included patients.
 
Per-Protocol (PP) population = all eligible patients (patients with no major violations of the inclusion/exclusion criteria) and evaluable patients (included treated patients with evaluation at 48 weeks or without evaluation at 48 weeks if progressive or dead patient).
 
Safety population = all treated patients who received at least one dose of treatment. All statistical analysis will be performed on ITT population, on PP population for efficacy analysis and on Safety population for safety analysis.

STUDY PERIOD	
 
❖ First inclusion: april 2019
 
❖ Inclusion period: 12 months Phase I + 12 months Phase II
 
❖ End of the inclusion period: march 2021
 
❖ Expected end of study: june 2022
 
❖ Report: september-december 2022
 
❖ Poster/public: phase I (2020), phase II (april 2023 and july 2023)
 

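### The phase II success rule of at least 29 of 65 has an exact one-sided type I error of 6.9% (5.2% by the normal approximation), not the stated 5%

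*Combined protocol and SAP*

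**What the plan says.** Section 10.1 (Phase II) opens "With a one-stage Fleming design" and gives alpha 5%, beta 20%, p0 = 35% and p1 = 50%. It concludes that "it would be necessary to include 65 evaluable patients (69 patients/ 5% non-evaluable patients").

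The null hypothesis is to be rejected with "at least 29 success (48 weeks disease control rate) out of 65 evaluable patients, the success rate is significantly greater than 35"%. The alternative is to be rejected with "28 or less success out of 65 evaluable patients, the success rate is significantly lower than 50"%. The synopsis (Statistical considerations) repeats the same rule.

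The plan does not say whether alpha is one-sided or two-sided, names no exact or approximate test, and gives no attained error rates. Section 10.3 adds only that the primary endpoint will be described as a percentage with a 95% confidence interval.

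**The concern.** A one-stage rule has two error rates, both fixed by n and the cut-off. If the cut-off is one too low for the stated alpha, the plan will call a result significant when it is not significant at the level promised.

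The trial is single-arm and this is its only formal efficacy test, so the cut-off alone carries the efficacy claim. With exactly 29 successes the report would state a rate significantly above 35%. Beside it would stand the confidence interval required by section 10.3, which includes 35%.

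**Working it through.** **Inputs (section 10.1):** p0 = 0.35, p1 = 0.50, alpha = 0.05, beta = 0.20, n = 65 evaluable, success if X ≥ 29. Sidedness is not stated. I take it as one-sided because the rule has one direction and because only that reading reproduces n = 65.

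**1. Sample size.** Normal formula: n = [(z_alpha √(p0(1−p0)) + z_beta √(p1(1−p1))) / (p1−p0)]².

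- One-sided 5%: [(1.645 × 0.4770 + 0.8416 × 0.5) / 0.15]² = [(0.7845 + 0.4208) / 0.15]² = 64.57, so 65. This agrees with the plan.
- Two-sided 5%: 81.7, so 82. This does not.
- Enrolment: 65 / 0.95 = 68.4, so 69. This agrees with the plan.

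**2. Cut-off on the same approximation.** Under p0 the mean is 65 × 0.35 = 22.75 and the standard deviation is √(65 × 0.35 × 0.65) = 3.845. The boundary is 22.75 + 1.645 × 3.845 = 29.08. The first integer at or above it is 30. The plan's 29 looks like 29.08 rounded down.

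**3. One-sided p-values by four methods.**

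| Method | 29/65 | 30/65 |
|---|---|---|
| Exact binomial | 0.069 | 0.041 |
| Normal, continuity-corrected | 0.067 | 0.040 |
| Mid-p | 0.055 | 0.033 |
| Normal, uncorrected | 0.052 | 0.030 |

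All four exceed 0.05 at 29, and all four are below it at 30.

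**4. Exact operating characteristics at n = 65.**

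| Rule | P(X ≥ r given 0.35) | P(X ≥ r given 0.50) |
|---|---|---|
| r = 29 (plan) | 6.9% | 83.9% |
| r = 30 | 4.1% | 77.1% |
| r = 31 | 2.4% | 69.0% |

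The plan's rule meets beta and misses alpha; r = 30 does the reverse. No cut-off at n = 65 meets both.

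**5. Interval at 29/65 (44.6%).** The exact 95% interval is 32.3% to 57.5%, and the exact one-sided 95% lower bound is 34.1%. Both include 35%.

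**6. The no-go side.** P(X ≤ 28 given 0.50) = 16.1%, within the stated beta of 20%. Only the word for significance is loose there, since the statement holds at the 20% level and not at 5%.

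**7. How often it matters.** The two rules differ only at X = 29. P(X = 29) is 2.8% at a true rate of 35% and 6.8% at 50%.

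**The case against.** The plan does not promise an exact test. On the uncorrected normal scale that produced n = 65, the p-value at 29 is 0.052 and the boundary is missed by 0.08 of a patient. Power is above the stated 80%, only one possible result changes, and the 95% interval in the report would itself show that 35% is not excluded. A reader could call this rounding in an early-phase trial.

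Much of that stands, and it limits the weight of the point. It does not rescue the rule: 29 fails on the plan's own approximation as well as on the exact test. The 6.9% is the real binomial error rate of the rule, whichever formula was used to plan it. Reading alpha as two-sided makes matters worse, because with 2.5% in the upper tail the exact cut-off is 31. An interval that contradicts the declared conclusion is a further reason to correct the text.

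It is also fair to say that changing the threshold or declared alpha of the primary endpoint is more than editorial. Section 13.6 may require a substantial modification request.

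**Conclusion.** The go rule is wrong as written. It has an exact one-sided type I error of 6.9% against a stated 5%, about 1.4 times the nominal level (6.9 / 5 = 1.38). A result of 29 of 65 cannot be called significantly greater than 35% at 5% by any of the four methods. The sample size, the enrolment figure and the beta side hold.

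The conclusion rests on the plan's own p0, p1 and n, and on reading alpha as one-sided, which is the reading most favourable to the plan. The practical effect is confined to a single outcome at n = 65. The text should be fixed before analysis, but the design is not undermined.

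**What to change.** In section 10.1 and the synopsis, state that alpha is one-sided and the test is exact binomial, and adopt one of these with its attained error rates:

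- **Option A.** *The combination is considered effective with at least 30 successes among 65 evaluable patients (exact one-sided alpha 4.1%, power 77.1%). With 29 or fewer, a rate above 35% has not been shown.* This gives up the stated 80% power.
- **Option B.** Keep 29, state alpha 6.9% and power 83.9%, and remove the claim of significance at 5%.

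Under either option, replace the statement that the rate is significantly below 50% with one that it has not been shown to exceed 35%.

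If the 5% level is kept, also give the cut-off for the number actually evaluable, which may not be 65:

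| Evaluable | Cut-off | Exact alpha | Power |
|---|---|---|---|
| 61 | 29 | 2.9% | 69.6% |
| 62 | 29 | 3.7% | 73.7% |
| 63 | 29 | 4.6% | 77.5% |
| 64 | 30 | 3.3% | 73.4% |
| 65 | 30 | 4.1% | 77.1% |
| 66 | 31 | 3.0% | 73.1% |
| 67 | 31 | 3.7% | 76.8% |
| 68 | 31 | 4.6% | 80.2% |
| 69 | 32 | 3.4% | 76.5% |

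The table needs one settled denominator. Section 2.2.1 uses all treated patients, while section 10.1 uses evaluable patients.

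**Cost.** A and B add no patients. They change text in section 10.1, the synopsis and the analysis plan still to be written, with a possible filing under section 13.6.

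If both 5% and 80% are required exactly, the smallest design is 31 of 68 evaluable. That means 68 / 0.95 = 71.6, so 72 enrolled, and a maximum of 90 instead of 87. It is fragile: at 69 to 72 evaluable, power at the exact 5% cut-off falls below 80% again (76.5%, 79.9%, 76.2%, 79.5%). I would therefore choose between A and B.

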### 10.3. STATISTICAL METHODS

A statistical analysis plan (PAS) will be written before the closed database. All statistical analyses will be performed on ITT population, on PP population for efficacy analysis and on Safety population for safety analysis. Populations are defined in section 10.2.

Descriptive analyses will be performed using median and range for continuous parameters, frequency and percentage for categorical variables.

Incidence rate of DLT and Incidence rates of adverse events and serious adverse events will be carried using frequencies and percentages at each dose level for phase 1.

The primary phase II endpoints 48 weeks disease control rates, will be described using percentage and its associated 95% confidence interval.

The median follow-up will be calculated using the reverse Kaplan-Meier method with its confidence interval of 95%.

All event free survival (PFS, OS) will be estimated using the Kaplan-Meier method, and then described using medians and rates with their associated 95% confidence interval.

Statistical analyses will be performed with STATA software (Stata Corporation, College Station, TX, USA).

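### The no-go sentence calls 28 or fewer successes of 65 significantly lower than 50%, but exact one-sided p at 28/65 is 0.16; the decision fits the design, the significance statement does not

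*Combined protocol and SAP*

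**What the plan says.** Section 10.1 (Phase II) plans the second part of the trial "With a one-stage Fleming design", with alpha 5% and beta 20%. The null rate is given as "the probability of inefficiency maximum) = 35" per cent and the target rate as "the probability of minimum efficiency) = 50" per cent. On size, "it would be necessary to include 65 evaluable patients (69 patients/ 5% non-evaluable patients").

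Two decision sentences follow. The go sentence sets the condition for rejecting p0 as follows: "if there are at least 29 success (48 weeks disease control rate) out of 65 evaluable patients, the success rate is significantly greater than 35" per cent. The no-go sentence declares the regimen insufficiently effective and the alternative rejected, with this condition and this claim: "if there are 28 or less success out of 65 evaluable patients, the success rate is significantly lower than 50" per cent. No significance level is attached to that last claim. The synopsis (Statistical considerations) carries the same two rules.

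Section 10.3 says that the primary Phase II endpoint "will be described using percentage and its associated 95% confidence interval". It plans no separate test against 50%, and it leaves further detail to a statistical analysis plan to be written later.

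**The concern.** The no-go sentence does two things. It makes a decision (the regimen is insufficiently effective), and it states what the data would show (a rate significantly below 50%). The second does not follow from the first. In a one-stage design with a single cut-off, every count below the go boundary leads to no-go, including counts that are compatible with both 35% and 50%.

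The adjoining go sentence uses the same word, significantly, for a comparison governed by alpha = 5%. A reader will carry that meaning into the mirror sentence. For counts just below the boundary, the protocol would then support a conclusion about the primary endpoint that the data do not carry. The 95% interval planned in section 10.3 would contain 50% beside it.

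**Working it through.** **Inputs (section 10.1):** n = 65 evaluable, p0 = 0.35, p1 = 0.50, alpha = 0.05, beta = 0.20, go at 29 or more, no-go at 28 or fewer. The sidedness of alpha is not stated.

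**1. Reproduce the sample size.** One-sample normal approximation:

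n = [(z(0.95)·√(p0(1−p0)) + z(0.80)·√(p1(1−p1))) / (p1−p0)]²
= [(1.645·√0.2275 + 0.842·√0.25) / 0.15]²
= [(0.7845 + 0.4208) / 0.15]² = 64.6, so 65.

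The figure is reproduced with a one-sided 5% alpha; a two-sided alpha gives 82. Then 65/0.95 = 68.4, so 69, as stated.

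**2. The no-go claim.** With X ~ Binomial(65, 0.50), the exact one-sided p against 50% for an observed count k is P(X ≤ k):

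| Successes k | Rate | P(X ≤ k), true rate 50% |
|---|---|---|
| 24 | 36.9% | 0.023 |
| 25 | 38.5% | 0.041 |
| 26 | 40.0% | 0.068 |
| 27 | 41.5% | 0.107 |
| 28 | 43.1% | 0.161 |

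At one-sided 5%, the rate is significantly below 50% only for 25 or fewer. It is not for 26, 27 or 28.

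**3. The interval.** Section 10.3 names no method; I assume exact (Clopper-Pearson). At 28/65 the 95% interval is 30.8% to 56.0% and the 90% interval is 32.6% to 54.0%. Both contain 35% and 50%.

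**4. The rule against the design's own limit.** P(X ≤ 28) at a true rate of 50% is 0.1605. This is the type II error, and power is 1 − 0.1605 = 0.8395. Since 0.1605 is below 0.20, the no-go decision meets the declared beta.

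**5. How often the affected counts arise.** The probability of 26 to 28 successes is 0.1605 − 0.0408 = 0.120 at a true rate of 50%. By the same subtraction it is 0.252 at 45% and 0.285 at 40%.

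**6. The go cut-off in the same paragraph.** With X ~ Binomial(65, p):

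| Go rule | Alpha, P(go) at 35% | Power, P(go) at 50% | Type II error |
|---|---|---|---|
| at least 29 | 0.069 | 0.839 | 0.161 |
| at least 30 | 0.041 | 0.771 | 0.229 |

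At n = 65, neither cut-off meets both declared limits exactly. The smallest exact design that does is 68 evaluable patients with go at 31 or more (alpha 0.046, power 0.802).

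**The case against.** The strongest reply is that the plan never attaches a 5% level to the no-go claim. In a two-hypothesis design, the error of wrongly rejecting the 50% alternative is beta, declared at 20%, and the rule's 16% is inside it. On that reading nothing has been miscalculated and no decision is wrong. This stands as far as the decision goes. It does not rescue the wording: the paragraph uses one word for a comparison at 5% and for another at up to 20%, without telling the reader.

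A second reply is that section 10.3 will print an interval showing that 50% is not excluded, and that the later analysis plan can settle the reporting language. That limits the harm, but it also means that section 10.1 and the planned interval would disagree.

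Two stronger readings are tempting and should not be drawn.

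- A reader might infer that the trial breaches a 5% error limit, with 16% in place of 5%, and would publish a significant finding of inefficacy. The documents set no 5% limit for this error and plan no test against 50%, so neither inference is supported.
- A reader might infer that a two-sided 95% interval beside a one-sided 5% rule is an error. At 30/65 the one-sided p against 35% is 0.041, while the 95% interval is 33.7% to 59.0% and contains 35%. That looks awkward, but section 10.3 uses the interval to describe the endpoint, and the decision rests on the count. It is a reporting choice.

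**Conclusion.** The significance statement in the no-go sentence is wrong as written, in section 10.1 and in the synopsis. At one-sided 5% it is unsupported for 26, 27 and 28 successes (p = 0.068, 0.107 and 0.161). Those counts together have a probability of 12% if the true rate is 50%, 25% if it is 45% and 29% if it is 40%. The no-go decision is sound under the declared beta.

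Severity is moderate: the defect concerns what may be concluded on the primary endpoint, and does not touch who is treated or whether the regimen goes forward.

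The result assumes exactly 65 evaluable patients, exact binomial tails, and that significantly carries the level used for the go claim. If the sponsor meant the 20% beta level, the statement is defensible at 28/65, but the level must be written down.

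The sentence cannot be corrected in isolation, because the go boundary beside it has exact one-sided alpha 0.069 and not 5%.

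**What to change.** In section 10.1 and the synopsis, delete the clause claiming a rate significantly below 50%. In its place write: *the null hypothesis of a rate of 35% or less is not rejected; the regimen is considered insufficiently effective under the design (type II error 16% if the true rate is 50%).*

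Reconcile this with the go sentence and restate the exact error rates for whichever cut-off is kept:

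- Go at 29 or more: alpha 0.069, power 0.839, type II error 0.161.
- Go at 30 or more: alpha 0.041, power 0.771, type II error 0.229. The no-go count becomes 29 or fewer, and the 16% above becomes 23%.

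Do not replace the clause with one that permits the significance claim at 25 or fewer. At 25/65 the exact 95% interval is 26.7% to 51.4% and still contains 50%, so claim and interval would again disagree.

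Optionally, in section 10.3, report the two-sided 90% exact interval beside the 95% one, labelled as the interval that matches a one-sided 5% test (at 30/65 it is 35.5% to 57.1%).

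The cost is a few words in two or three places and a weaker no-go statement. Conduct is unchanged, and so are patient numbers at n = 65. Holding both declared limits exactly would need 68 evaluable patients, or 68/0.95 = 71.6, so 72 included instead of 69.
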